### **Magnetic Resonance Imaging (brain structure and activation)**

The fMRI protocol will be performed using an MRI scanner employing pulse sequences and hardware that have been approved by the FDA for human clinical use. The field strength is 3 Tesla and all relevant operating characteristics (RF power deposition, rate of change of the field gradients, coil design) fall within the limits of FDA guidelines for NMR exposure. Participants will be carefully screened to exclude those who may have metal in or on their bodies that cannot be removed (e.g., bullets, metal filings, body piercings, etc.). MR facility rules strictly forbid staff from entering the magnet room carrying metal objects. The risk of claustrophobia is minimized by screening subjects for

self-reported claustrophobia and making sure the subject is lying comfortably with head and neck supported and providing ear protection with headphones, a mirror to see out, a button to signal distress, and an intercom. Scan time will be kept to a minimum. Female participants will be given a urine pregnancy test immediately before the scanning period, and those with a positive result will not be scanned. Participants are given a squeeze ball to use in case of an emergency. Participants are informed that if they experience any unpleasant sensations or are otherwise uncomfortable, they can alert the MRI technologist via the squeeze ball and the technologist will stop the scan immediately.

With regard to subject confidentiality, all records will be coded, stored in a locked cabinet, and kept strictly confidential. Samples stored in the freezer will all be coded; names will not appear on samples. Our database will be password protected, as is the computer that the database resides on. Subject names do not appear in the database, just a subject ID number. The list linking the ID number with the subject name is kept in a separate, locked filing cabinet. Thus, breaches of confidentiality are very unlikely.

University policy requires that all study personnel complete human subjects training. Thus, the PIs, study coordinator, and graduate students involved in this data collection have all had this training. While the risk of medical emergency is very low, all subject personnel are certified in CPR. The Nurse Managed Health Center is located across the hallway from the research laboratory. An automated external defibrillator is located on site, and emergency numbers are posted on the phone and in the laboratory. Christiana Care Hospital, a 913-bed teaching hospital, is located 4 miles from the University.

## **MRI ACQUISITION AND ANALYSIS AND STATISTICS**

### ***MRI Acquisition***

We will use a 3T MRI Siemens Prisma Scanner and 64-channel head coil to obtain all brain images. Padding will be placed around the participant's head to minimize head motion. Participants will be instructed to keep both their head and the rest of their body as still as possible.

All participants will undergo a T1-weighted anatomical scan [repetition time (TR) = 2080 ms; echo time (TE) = 4.6 ms; field of view = 210 x 210 mm; voxel size = 0.7 mm^3; slice thickness = 0.7 mm] followed by two BOLD fMRI scans (baseline & infusion). Functional scans will be acquired using a multi-band gradient-echo echo-planar imaging (EPI) sequence [TR = 829 ms; TE = 40 ms; flip angle = 52°; field of view = 208 x 208 mm; voxel size = 2.0 mm^3; slice thickness = 2.0 mm]. During functional scans, participants will be instructed to keep their eyes open and fixated on a white cross (on a black screen) to minimize the effects of eye motion and ensure the reliability and consistency of our results. These sequences are identical to those used in our group's pilot study.

### ***MRI Analysis***

The preprocessing steps described here were also utilized in our group's pilot study. Functional MRI images will be converted and analyzed using several software packages including MRIcroGL, AFNI (Analysis of Functional NeurolImages) and FSL (FMRIB Software Library). Initially, the 30-minute infusion fMRI scans will be split into an early phase (0-15 minutes) and late phase (15-30 minutes). Processing steps include: 1) despiking of the resting-state fMRI scans to eliminate outliers, 2) slice-timing correction of the fMRI scans, 3) 3D rigid motion correction to a reference frame to correct for head motion in the resting-state data (we removed time points with head motion > 0.5 mm), 4) cleaning the fMRI data using ANATICOR (accounting for the 6 motion parameters, white matter, and CSF signal), 5) band-pass filtering (0.008 to 0.10 Hz) (42), 6) skull-stripping of the T1-anatomical scan using FSL, 7) co-registration (i.e., alignment) of the T1-anatomical and functional scans, 8) normalization of all scans to the 1mm MNI152 template, and 9) spatial smoothing of the resting-state data using a Gaussian kernel of full-width half maximum (FWHM) = 4mm. These smoothing dimensions align with recommendations to choose a Gaussian kernel of FWHM double the voxel size (which was 2 mm^3 for this study) and are appropriate for smaller brain structures like the SFO and OVLT.

The ROIs for this study will be defined as follows. The SFO and OVLT will be defined as a 2-mm radius spheres based on previous studies. The Montreal Neurological Institute

(MNI) coordinates corresponding to the center of each ROI are: SFO: x = 0 mm, y = 2 mm, z = -6 mm and OVLT: x = 0 mm, y = 2 mm, z = -12 mm. The location of these seeds has been verified using Duvernoy's Atlas of the Human Brainstem and Cerebellum and these ROIs are consistent with those used in a pilot study conducted in our lab.

Following pre-processing, we will conduct seed-to-seed functional connectivity analyses to assess the synchronization of the spontaneous low frequency fluctuations in the BOLD signal between our ROIs. We will calculate functional connectivity between the SFO and OVLT. Pearson correlations will be computed between the ROIs for the seed-to-seed functional connectivity analysis. Pearson correlations will be converted to Z-scores using a Fisher's transform which will be statistically analyzed, as in our pilot study.

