### ***Hypertonic Saline Infusion***

A 3% NaCl hypertonic saline will be infused at a rate of  $0.15 \text{ ml} \cdot \text{kg}^{-1} \cdot \text{min}^{-1}$  into the participant's arm for 30 minutes total while participants are in the MRI scanner. The hypertonic saline will be purchased from a manufacturer and will be prepared by the registered nurse. The volume of hypertonic saline in the tubing will be closely monitored by the registered nurse to ensure that participants are receiving the correct amount of saline. The volume infused and infusion rate is similar to previous studies infusing saline, which we have previously published (Farquhar et al AJP-Heart 2006). The 3% hypertonic saline is expected to raise blood sodium concentration and plasma osmolality approximately 1-2%. Blood samples will be taken pre- and post-infusion to measure changes in blood sodium concentration and osmolality.

***MRI Scan.*** The MRI scan will take approximately 1 hour (Figure 2). The subject will be free to stop at any time, either by indicating their desire to do so directly to the investigator or by squeezing a ball while in the MRI scanner that alerts the technologist who is running the machine.

- ***MRI Screening Form.*** Participants will again fill out the MRI screening form prior to the scan to ensure they can safely undergo MRI.
- ***Structural and BOLD MRI.*** During all scans the subjects will wear disposable earplugs and headphones to reduce scanner noise. Participants may also be asked to wear a pulse oximeter on their finger to measure heart rate or a respiratory belt around their chest to measure breathing. Both devices are provided by Siemens with the MRI scanner, are MR-safe and MR-compatible, and interface with the MRI scanner software. Participants will also wear an FDA-approved MRI compatible blood pressure cuff on their middle finger throughout the scan that measures blood pressure through a Pulse Decomposition Analysis. This device is made through BioPac Systems and is MR-safe and MR-compatible.

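### At a TR of 829 ms, heart rates of 66.4–71.9 or 72.9–78.4 bpm fold into the analysed 0.008–0.10 Hz band; control is partial, the pulse oximeter is optional, and no cardiac-phase sensitivity analysis is planned

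*Combined protocol and SAP*

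**What the plan says.** MRI Acquisition sets an anatomical scan "followed by two BOLD fMRI scans (baseline & infusion"), the functional ones with an "echo-planar imaging (EPI) sequence [TR = 829 ms".

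MRI Analysis lists nine processing steps. Step 4 is "cleaning the fMRI data using ANATICOR (accounting for the 6 motion parameters, white matter, and CSF signal"). Step 5 is "band-pass filtering (0.008 to 0.10 Hz"). The section adds: "The preprocessing steps described here were also utilized in our group's pilot study." The only connectivity measure specified is the SFO–OVLT Pearson correlation, Fisher-transformed. Statistical Analysis compares it across baseline, early and late infusion, with and without furosemide.

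On physiological recording, the Structural and BOLD MRI item under Hypertonic Saline Infusion says: "Participants may also be asked to wear a pulse oximeter on their finger to measure heart rate or a respiratory belt". It adds: "Both devices are provided by Siemens with the MRI scanner, are MR-safe and MR-compatible, and interface with the MRI scanner software." A separate device is not optional: participants will wear a "blood pressure cuff on their middle finger throughout the scan that measures blood pressure through a Pulse Decomposition Analysis".

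MRI Acquisition, MRI Analysis and Statistical Analysis give none of these recordings a role. They name no cardiac regressor, heart-rate covariate or related sensitivity analysis.

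**The concern.** A resting heartbeat is faster than half the sampling rate of these scans, so it appears in the data at a false, lower frequency. For some ordinary heart rates that false frequency lies inside the band the plan keeps. Folding happens when the image is sampled, so a later filter cannot tell folded pulsation from slow BOLD fluctuation.

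The whole connectivity result rests on one correlation between two spheres of 2-mm radius. If both carry leftover pulsation, their correlation partly reflects the pulse. A contrast between phases or visits is biased if that contribution changes on balance between them. If it changes in no consistent direction, the main cost is extra within-subject noise.

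The Risks and Benefits section says blood pressure may rise during hypertonic saline and may fall after furosemide. It says nothing about heart rate, but a constant cardiac state across the compared conditions cannot be taken for granted. As written, a scan with no oximeter trace complies with the protocol, and a trace that was never recorded cannot be recovered later.

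**Working it through.** **Inputs from the documents.** TR = 0.829 s (MRI Acquisition); retained band 0.008–0.10 Hz (MRI Analysis, step 5); infusion phases of 15 minutes = 900 s (MRI Analysis). The plan states no aliasing figure to reproduce.

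**Step 1: sampling rate.** fs = 1/0.829 = 1.2063 Hz. Half of this is 0.603 Hz, or 36.2 bpm, so a resting pulse is undersampled.

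**Step 2: affected heart rates.** A fundamental at frequency f near fs appears at |f − fs|. It falls in the retained band when 0.008 ≤ |f − fs| ≤ 0.10.
- Below fs: 60 × (1.2063 − 0.10) to 60 × (1.2063 − 0.008) = 66.4 to 71.9 bpm.
- Above fs: 60 × (1.2063 + 0.008) to 60 × (1.2063 + 0.10) = 72.9 to 78.4 bpm.

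Simulated pure tones sampled at 0.829 s for 900 s agree. Rates of 66.5, 69, 71.8, 73, 75 and 78.3 bpm appear in band; 60, 66, 72.4, 79 and 85 bpm do not. Rounding of the TR (828.5–829.5 ms) moves the limits by at most 0.05 bpm. The second harmonic also folds in at 69.4–72.1 and 72.6–75.4 bpm, which largely overlaps the ranges above, and at about 105.6–111.6 bpm.

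**Step 3: share of scans exposed.** The documents give no heart rates, so this step rests on an assumption: mean rates per scan are normal with mean m and standard deviation s. P(m) is the probability of a mean rate in either range. The net change for an assumed 5-bpm rise is P(m + 5) − P(m).

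| s (bpm) | P at m = 60 / 65 / 70 / 75 | Net change for +5 bpm |
|---|---|---|
| 6 | 0.135 / 0.366 / 0.587 / 0.580 | +0.231 / +0.220 / −0.007 / −0.227 |
| 10 | 0.211 / 0.326 / 0.403 / 0.401 | +0.115 / +0.078 / −0.002 / −0.081 |
| 12 | 0.216 / 0.295 / 0.345 / 0.343 | +0.079 / +0.049 / −0.001 / −0.051 |

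Over these cases 14–59% of scans have a mean rate in an affected range. The net change runs from −23 to +23 percentage points and is close to zero at m = 70.

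**Step 4: cost of extra regressors.** A 15-minute phase has 900/0.829 ≈ 1,086 volumes. Treating in-band samples as independent, there are 2 × (0.10 − 0.008) × 900 = 165.6 of them. In the worst case each of k added regressors costs one, so SE(z) = 1/√(165.6 − 3 − k). This gives 0.078 for k = 0, 0.079 for k = 4, 0.080 for k = 8 and 0.081 for k = 12. The existing nuisance regressors are ignored here.

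**The case against.** The strongest reply is that nothing here shows an error in the result. What matters is how much cardiac variance remains in the SFO and OVLT after cleaning, and the documents do not say. On assumed inputs even the direction of any net change is undetermined. This stands, and it limits the point to exposure.

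White matter and CSF signals are sampled at the same TR, so pulsation in them folds to the same frequencies and step 4 removes the shared part. This also stands: control is partial, not missing. How much is left in two very small regions is unknown.

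A reader might infer that no pulse-related recording is assured. The documents do not support that, since the finger cuff is worn throughout and works by a pulse-based method. Optional describes the oximeter only. The documents do not say, however, that the cuff yields usable pulse timing or that its output enters the image cleaning.

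A reader might also class each scan as in or out of band and count how many switch between phases. That would assume one constant heart rate per scan, which nothing in the documents supports. With an assumed within-scan SD of 3 bpm, a scan averaging 72.4 bpm, nominally between the two ranges, spends about 83% of its time in band; one averaging 69 bpm spends about 74%. Switching counts should not be used.

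Finally, the team may say that the pipeline matches the pilot. That is a good reason to keep it as the main analysis. It does not answer the point, because the same TR, band and nuisance model carry the same exposure.

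**Conclusion.** The point holds as a modest, cheap improvement. The folding limits follow from the plan's own TR and filter band. The plan relies on motion, white matter and CSF regression alone, and it allows scans without an oximeter trace.

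The 14–59% and the −23 to +23 points rest on assumed heart rates (means of 60, 65, 70 and 75 bpm; SDs of 6, 10 and 12; a 5-bpm rise) and describe mean rates per scan. They measure neither bias nor error in Fisher z. A reader might infer that a phase or furosemide effect would be a cardiac artefact. The documents do not support this: they give no heart rates, report no heart-rate change and give no size of pulsatile signal in either region. What can be said is that the plan as written does not ensure that the team could test that possibility.

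**What to change.** 1. **Recording** (Structural and BOLD MRI item under Hypertonic Saline Infusion). Make the scanner-supplied pulse oximeter standard for the baseline and infusion scans at both MRI visits.
2. **Processing** (MRI Analysis). Keep the pilot-consistent pipeline as the main analysis. Prespecify one sensitivity analysis that adds RETROICOR-type cardiac-phase regressors, with their timing computed to match slice acquisition and the slice-timing correction in step 2.
3. **Comparison** (Statistical Analysis). Run the planned comparison with and without these regressors on the same scans, namely those with a usable pulse trace, so that a loss of scans is not mistaken for a cardiac effect. Report both beside the full-sample main result, and give the number of usable traces by phase and visit.
4. **Interpretation.** State in advance that a phase or furosemide effect not retained after the cardiac regressors are added will be reported as possibly cardiac in origin.

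The cost is minor set-up with a sensor that comes with the scanner, one extra processing run, some scans lost from the sensitivity analysis only, and the small rise in standard error shown in step 4 of the working. The main analysis does not change.

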### ***Statistical Analysis***

Normality will be verified using Shapiro-Wilk tests. Normally distributed baseline characteristics will be reported as frequencies and mean standard deviation. Two-way repeated measures analysis of variance (ANOVA) models will be used to assess changes in functional connectivity between baseline, the early phase (0-15 min) of the infusion, and the late phase (15-30min) of the infusion with and without furosemide prior. If data are non-normally distributed, aligned rank transformations (ARTs) will be conducted prior to performing two-way repeated measures ANOVAs. ARTs will be completed using ARTTool2 (version 2.2.2) or ARTTool integrated into R. Significant main effects of time and time\*sex interactions will be followed with pairwise post-hoc comparisons corrected for multiple comparisons.

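### Does smoothing at 4 mm before correlating two seeds 6 mm apart undermine the SFO–OVLT connectivity result?

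*Combined protocol and SAP*

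**What the plan says.** All of this is in the combined protocol and SAP, under MRI Acquisition and Analysis and Statistics.

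- **Smoothing.** The ninth and last pre-processing step in MRI Analysis is "spatial smoothing of the resting-state data using a Gaussian kernel of full-width half maximum (FWHM) = 4mm". The section gives its reasons: the width is twice the 2 mm voxel, and such dimensions "are appropriate for smaller brain structures like the SFO and OVLT". It also says that the pilot study used the same steps.
- **Seeds.** "The SFO and OVLT will be defined as a 2-mm radius spheres based on previous studies". The centres are "SFO: x = 0 mm, y = 2 mm, z = -6 mm" and "OVLT: x = 0 mm, y = 2 mm, z = -12 mm".
- **Outcome.** "We will calculate functional connectivity between the SFO and OVLT". This is the only pair named. The Pearson correlation is computed after pre-processing, hence on smoothed data, and is then Fisher-transformed.
- **Test.** Statistical Analysis describes a two-way repeated-measures ANOVA of changes between baseline, the early phase and the "late phase (15-30min) of the infusion with and without furosemide prior".

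Neither section includes an analysis without the smoothing step.

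**The concern.** The two seeds are small and close together, and the kernel is as wide as a seed. After smoothing, each seed average is mostly built from signal outside its own sphere, and part of that signal is common to both. A correlation can then appear between structures that are not connected. The stated reasons for the kernel concern voxel size and structure size; they do not address the distance between the two regions being correlated.

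At stake would be the study's only named connectivity outcome. If the kernel-made part of the correlation differed between baseline and infusion, or between the furosemide and control visits, the ANOVA could pick up a processing artefact and report it as a change in connectivity. With no unsmoothed analysis planned, a reader could not see how far the result depends on that step.

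**Working it through.** **Inputs from MRI Acquisition and MRI Analysis:** 2 mm voxels; 4 mm FWHM; 1 mm template grid; sphere radius 2 mm; centres (0, 2, −6) and (0, 2, −12); 15-minute phases; pass band 0.008 to 0.10 Hz. **From Study Population and Recruitment:** 50 participants. The documents do not give the spatial noise structure, the interpolation method or the between-subject variation, so results that need them are shown as ranges.

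**1. The plan's own figure.** Twice the voxel size: 2 × 2 mm = 4 mm. It reproduces.

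**2. Geometry.** Centre distance |−6 − (−12)| = 6 mm. Edge gap 6 − 2 × 2 = 2 mm. The spheres do not overlap.

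**3. Kernel-made correlation at zero connectivity.** Kernel sigma = 4 / 2.355 = 1.70 mm. Let A and B be the two sphere-average weights (33 grid points each) after smoothing. For spatially independent noise, r = ΣAB / √(ΣA² · ΣB²).

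| Noise model | Smoothed r | Unsmoothed r |
|---|---|---|
| Independent on 1 mm grid | 0.089 | 0.000 |
| Independent 2 mm voxels, nearest-neighbour resampling | 0.103 | 0.000 |
| Independent 2 mm voxels, linear resampling | 0.118 to 0.134 | 0.000 to 0.004 |
| Intrinsic smoothness 2 / 3 / 4 mm (assumed) | 0.13 / 0.18 / 0.25 | 0.003 / 0.026 / 0.089 |

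About 21% of a smoothed seed's weight lies in its own sphere and about 0.4% in the other sphere. So there is almost no direct leakage from one seed to the other; the shared part comes from the gap and its surroundings.

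**4. Does it reach the planned tests?** The same A and B apply in every phase and condition. If noise variance rises everywhere by a factor k, that factor multiplies ΣAB, ΣA² and ΣB² alike and cancels, so the kernel-made r stays at 0.089. At zero connectivity the offset changes only if the noise changes its spatial pattern, for example by rising in the gap and not elsewhere.

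**5. Size of such a change.** Noise variance is raised only in the planes z = −10 to −8 (assumed), with the outer two planes counted at half to full weight. The starting Fisher z is 0.0890.

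| Rise confined to the gap | r | Change in z |
|---|---|---|
| 10% | 0.0927 to 0.0942 | 0.0039 to 0.0054 |
| 25% | 0.0984 to 0.1020 | 0.0097 to 0.0134 |
| 100% | 0.125 to 0.137 | 0.037 to 0.049 |

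**6. Yardstick.** Effective sample size per phase = 2 × 900 s × (0.10 − 0.008) Hz = 165.6. SE(z) = 1/√(165.6 − 3) = 0.0784. For 50 participants with no lost frames, no dropout and no between-subject variation:

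- difference between two phases: 0.0784 × √2 / √50 = 0.0157;
- phase-by-furosemide contrast: 0.0784 × 2 / √50 = 0.0222;
- furosemide effect averaged over the two infusion phases: 0.0784 / √50 = 0.0111.

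For a 10 to 25% rise, the ratios are 0.0039/0.0157 = 0.25 to 0.0134/0.0157 = 0.85 for the first contrast, 0.18 to 0.60 for the second and 0.35 to 1.21 for the third. These standard errors are lower bounds for their contrasts, so the true ratios are smaller.

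**The case for a change.** The best case for the concern is that stable local noise across saline and furosemide states is itself an assumption, that the whole connectivity outcome rests on one closely spaced pair, and that one more extraction from existing scans costs little. A doubling of noise confined to the gap would shift z by 0.037 to 0.049, or 2.4 to 3.1 of the 0.0157 standard error. With assumed intrinsic smoothness of 2 to 3 mm, a 25% rise in the gap moves the smoothed r by 0.013 to 0.021 and the unsmoothed r by only 0.0005 to 0.005. A larger assumed swing, of 0.3 in the share of seed variance that is local noise, would change the kernel-made part by 0.3 × 0.087 = 0.03 to 0.3 × 0.25 = 0.08.

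What stands is the geometry, the offset, and the fact that an unsmoothed run would be less sensitive to this one route. What does not stand is the step from there to a defect. Nothing in the documents supports a doubling confined to a 2 mm gap or a swing of 0.3, and the ANATICOR step regresses out motion, white-matter and CSF signal before smoothing, which works against this route even if incompletely.

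Nor would the unsmoothed run settle the matter. It is noisier: about 6 times the noise variance under nearest-neighbour resampling, 4.4 to 5.0 times under linear. It also attenuates true correlation on a different scale: in a model with true r = 0.5, 2 mm smoothness and noise equal to signal, smoothed r is 0.297 and unsmoothed 0.385. Doubling the noise lowers both, to 0.236 and 0.313, so agreement would not exclude a noise effect. With 3 mm smoothness and noise five times signal, the same doubling takes smoothed r from 0.203 to 0.194 and unsmoothed from 0.155 to 0.100, so disagreement would not implicate the kernel. If the data call for the planned aligned rank transform, the ANOVA also yields no Fisher-z estimate to set beside the main one.

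**Conclusion.** The concern does not hold. Smoothing does create a small positive correlation between unconnected seeds, about 0.09 to 0.13 without any intrinsic smoothness and up to 0.25 with an assumed 4 mm. But the kernel is prespecified, justified, carried over from the pilot and identical in every cell of the design. The planned tests concern within-subject change, where a stable offset largely cancels, and the plan nowhere proposes to read the level of the correlation as a finding.

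Bias in the contrasts would need a change in the spatial pattern of noise. At an assumed 10 to 25% rise in the gap the shift is 0.004 to 0.013 in z. This is below one lower-bound standard error for the comparison of two phases and for the phase-by-furosemide contrast, and at most 1.2 for a furosemide effect averaged over both infusion phases. An unsmoothed run would be a matter of preference, and its result could be read either way.

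This rests on roughly stable spatial noise patterns across phases and visits, and on the documents' silence about intrinsic smoothness and interpolation, which is why the offsets are ranges and not predictions.
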